17.5 Responsibility of the Data Manager

The primary responsibility of data manager is to enter data from case report forms (CRFs) to computed database. The data manager is responsible for collecting all source documentation and worksheets prepared by all members of the research team and then transcribing the data on to the appropriate collection tool for submission to the sponsor.

Specific responsibilities include but are not limited to the following:

- Source document archiving after receiving from CRA.
- File and pull study records
- Case report form design, design CRF completion guidelines and its entry by assigned personnel
- Review data for accuracy and completeness
- Clarify data with research staff as necessary
- Enter data into the computer
- Correct/revise data as appropriate
- Maintain back-up system for computerized data

18 Audit and Inspection

An audit/inspection may be carried out by qualified sponsor staff, by subcontracted auditors or by representatives of national or foreign health authorities to ensure that the study is conducted as per protocol and in accordance with regulatory requirements, and to ensure the validity of the data.

Participation in this study implies acceptance to cooperate in any potential audit/inspection. Audit/inspection may take place after the end of the study.

19 References

- 1- Sartelli M. A focus on intra-abdominal infections. *World J Emerg Surg.* 2010; 5:9.
- 6 - Barie PS. Management of complicated intra-abdominal infections. *J Chemother* 1999;11:464-77.

Table 4	Number and percent of Adverse Event necessitating a change or discontinuation of treatment among treatment groups	18
Table 5	Number and percent of Serious Adverse Event among treatment groups	18
Table 6	Number and percent of causes of treatment discontinuations among treatment groups	19
Table 7	Number and percent of Adverse Event necessitating a change or discontinuation of treatment among treatment groups	19
Table 8	Number and percent of Adverse Event among treatment groups	19
Table 9	Number and percent of complete resolution for pelvi- abdominal infection among treatment groups	20
Table 10	Number and percent of complete healing of the post-operative wounds among treatment groups	20
Table 11	Number and percent of signs/symptoms of post-operative wound infection among treatment groups	21
Table 12	Percent Change in Total leukocytes among treatment groups	22
Table 13	Percent Change in SGOT among treatment groups	23
Table 14	Percent Change in SGPT among treatment groups	23
Table 15	Number and percent of complete resolution, improvement, failure or relapse for Pelvi- abdominal infection among treatment groups	24
Table 16	Percent Change in mean days for complete healing of post-operative wounds after 8 days of treatment (Follow up 1 visit) among treatment groups	25
Table 17	Percent Change in mean days for complete healing of post-operative wounds after 15 days of treatment (Follow up 2 visit or End of study visit) among treatment groups	25

1 Study Objective:

1.1 Primary Objectives:

1.1.1 Primary Safety:

To compare safety of oral Ciprodiazole[®] tablets (Ciprofolxacin/Metronidazole) versus currently used Ciprofloxacin[®] tablets & Metronidazole[®] tablets in pelvi-abdominal infections, either non-operative or post-operative following IV antibiotics.

1.1.2 Primary efficacy:

To compare efficacy of oral Ciprodiazole[®] tablets (Ciprofolxacin/Metronidazole) versus currently used Ciprofloxacin[®] Tablets & Metronidazole[®] tablets in pelvi-abdominal infections, either non-operative or post-operative following IV antibiotics

1.2 Secondary Objectives:

1.2.1 Secondary Safety:

- Presence of any signs/symptoms of post-operative wound infection such as redness, fever or wound discharge.
- Presence of undesirable effects on total leukocyte count and liver enzymes (SGOT & SGPT)

1.2.2 Secondary efficacy:

- To compare the complete resolution or improvement of Pelvi-abdominal infection between ciprodiazole[®] versus combined treatment, based on pelvi-abdominal ultrasound and others
- To compare the days for complete healing of post-operative wounds between ciprodiazole[®] versus combined treatment

2 Study Design

This is a single center, open Label, controlled, interventional phase IV Study conducted in Menoufia University Hospital in Egypt to compare the safety and efficacy of oral Ciprodiazole[®] tablets (Ciprofloxacin/Metronidazole) versus currently used Ciprofloxacin[®] Tablets & Metronidazole[®] tablets in pelvi-abdominal infection and following IV antibiotics in post-operative period, for pelvi-abdominal surgeries or acute conditions

This study is a clinical trial that will enroll 312 patients, who had pelvi-abdominal infection and/or started IV antibiotics for 48 hours, post-operative or till be able to tolerate oral intake in post-operative period, for pelvi-abdominal surgeries. They will be divided into two

treatment groups; group A: patients are treated with Ciprofloxacin® tablets (Ciprofloxacin/Metronidazole) and group B (control group): patients are treated with the currently used Ciprofloxacin® Tablets & Metronidazole® tablets, using computer-generated randomization list, generated by the Data Management department (DM) of the CRO (Nagy Research) for the 2 groups who will be enrolled in this study will agree to the release of information and sign an informed consent. Subjects included in this study are enrolled for the collection of data that reflect the care they receive under routine clinical circumstances. All provided care should be according to protocol and the local standard of medical care.

The screening and enrollment period is planned to be 12 months. Subject will start receiving the treatment for a duration not exceeding 15 days. And with post-operative cases, subject will start receiving the treatment after IV antibiotics for 48 hours or till be able to tolerate oral intake. Follow up will be for 15 days from enrolment till End of treatment.

3 Study Setting

Subjects will consent to the collection of study related information while on the study. Subjects will be informed that data will be collected about their health while they are enrolled in this study. They may choose to withdraw at any time. Subjects will be advised that data collected in this study will be provided to the Sponsor, and may be reported to regulatory authorities or published in scientific journals. In any of these events, the subjects' identities will not be revealed.

3.1 Inclusion Criteria:

Subjects meeting all of the following criteria will be considered for enrolment in the study:

1. Egyptian male and female patients aged between 18-65 years' old
2. Subjects having pelvi-abdominal infections such as and not limited to: Ulcerative colitis, Diverticulitis, Cholecystitis, and PID (e.g oophoritis and salpingo-oophoritis).
3. Subjects during post-operative period for pelvi-abdominal surgery and following IV medication with Metronidazole injection plus third generation cephalosporin.
4. Subjects who are willing to sign Informed Consent Form (ICF) and ready to comply with the protocol for the duration of the study

3.2 Exclusion Criteria:

Subjects presenting with any of the following will not be included in the study:

1. Subjects with a history of hypersensitivity to any of the active ingredients of the treatments used

2. Subjects who are receiving or received any other antibiotics during the previous two weeks, rather than IV treatment in the first post-operative 48 hours, mentioned in the protocol (Metronidazole injection plus third generation cephalosporin)
3. Subjects with Pelvi-abdominal infection and performed surgery after failure of oral antibiotics.
4. Subjects having surgeries such as colorectal surgeries, appendectomy and ovarian cystectomy
5. Subjects with any medical condition requiring the usage of the following medications:
 - a. Drugs that induce microsomal liver enzymes, such as Phenytoin or Phenobarbital, may accelerate the elimination of metronidazole
 - b. Drugs that decrease microsomal liver enzymes activity, such as cefrimide, may prolong the half-life and decrease plasma clearance of metronidazole.
 - c. Administration of theophylline in combination with Ciprofloxacin[®] may lead to cardiac arrest, seizures, status epilepticus, and respiratory failure
 - d. Administration of corticosteroids in combination with Ciprofloxacin[®] may lead to tendinitis
 - e. Antacids containing magnesium and aluminum, supplements and other products containing calcium, iron or zinc as they reduce the effect of Ciprofloxacin[®].
 - f. Tizanidine because this may cause low blood pressure and sleepiness
6. Subjects with uncontrolled diabetes mellitus; FBG > 200 mg/ml
7. Subjects with renal impairment (S. Creatinine > 1.5 mg/dL)
8. Subjects with hepatic impairment (Child-Pugh Score B-C)
9. Subjects with liver enzymes (SGOT, SGPT) > 2 times Normal range.
10. Pregnant or breast-feeding women

4 Medicinal Products:

- Ciprofloxacin[®] Tablets (Ciprofloxacin hydrochloride 500 mg & Metronidazole 500 mg)

5 Endpoints:

5.1 Primary Endpoints:

5.1.1 Primary Safety:

Incidence of serious/non-serious adverse events

5.1.2 Primary Efficacy:

- Complete resolution for pelvi-abdominal infection based on pelvi-abdominal ultrasound and others and/or clinical response
- Complete healing of post-operative wounds

5.2 Secondary Endpoints:

5.2.1 Secondary Safety:

- Presence of any signs/symptoms of post-operative wound infection such as redness, fever or wound discharge.
- Change in Total leukocytes count and Liver enzymes (SGOT, SGPT), between baseline (visit 1) to End of study visit (Follow up 2 visit)

5.2.2 Secondary Efficacy:

- Describe complete resolution, improvement, failure or relapse of pelvi-abdominal infection based on pelvi-abdominal ultrasound and others and or clinical response.
- Days for complete healing of post-operative wounds after 8 days of treatment (Follow-up 1 V) & 15 days of treatment (End of study visit) between the 2 groups

6 Assessment Schedule

Subjects will be enrolled for 12 months including screening visit

- Visit 1: Screening and treatment initiation visit, Day 0
- Follow-up 1 visit: Day 8 (+/-) 3 days
- Follow-up 2 visit & End of study visit: Day 15 (+/-) 3 days

7 Study Size:

Subjects having pelvi-abdominal infection, in post-operative period of pelvi-abdominal surgeries or acute conditions will be selected from the surgical department in Menoufia University Hospital and some subjects might be referred from other departments in Menoufia University Hospital such as and not limited to; the department of Gynecology and Obstetrics. Patients will be asked to participate in the study and sign the informed consent, then screening for inclusion and exclusion criteria will be done and recorded in the patient's medical records (either enrolled or screening failure).

7.1 Determination of Sample Size:

8.1 Analysis populations

Analysis of all efficacy variables will be performed only for patients who completed the study without protocol violation (as per protocol).

Analysis of all safety variables will be performed for all patients (intent-to-treat population), who received even 1 dose of the treatment; either Ciprofloxacin[®] tablets or currently used Ciprofloxacin[®] Tablets & Metronidazole[®] tablets.

8.2 Statistical methods

This section provides specifications for preparation of final Statistical Analysis Plan (SAP), which will be issued prior to database lock. Any differences compared to this statistical section should be identified and documented in final SAP. Analysis will be done using SPSS version 21.

8.3 Analyses variables

8.3.1 Descriptive Analysis:

- Descriptive analysis of the collected data. All enrolled patients will be included in the safety analysis.
- All quantitative primary and secondary end point variables will be described
- Data from primary and secondary endpoints will be summarized using appropriate summary statistics i.e. n (number of subjects), mean, Standard Deviation (SD), median and range.

8.3.2 Comparative Analysis:

- All tests will be performed on the 5% level of significance.
- Chi² test for unpaired categorical variables.
- Paired t-test to estimate the change in numerical variables throughout the study visits.
- Student t-test to estimate the comparison between the subgroups for the numerical variables.
- P-values less than 0.05 will be considered statistically significant

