Frequency distribution (number & percent) of presence of any signs/symptoms of post-operative wound infection such as redness, fever or wound discharge. Chi² test will be used to determine *p*-value and significance between the 2 groups.

B. Change in Total leukocytes count between baseline (visit 1) to End of study visit

Descriptive analysis (mean, Standard Deviation, Median, Interquartile Range, Minimum and Maximum) of total leucocyte will be from baseline (visit 1) to End of study visit. Percent change will be calculated between baseline to End of study. Paired t-test will be used to determine *p*-value and significance between baseline and at the end of the study. Unpaired t-test will be used to determine the *p*-value and significance between Changes in total leucocyte between 2 groups.

C. Change in Liver enzymes (SGOT) between baseline (visit 1) to End of study visit

Descriptive analysis (mean, Standard Deviation, Median, Interquartile Range, Minimum and Maximum) of Liver enzymes (SGOT) will be from baseline (visit 1) to End of study visit. Percent change will be calculated between baseline to End of study. Paired t-test will be used to determine *p*-value and significance between baseline and at the end of the study. Unpaired t-test will be used to determine the *p*-value and significance between Changes in Liver enzymes (SGOT) between 2 groups.

D. Change in Liver enzymes (SGPT) between baseline (visit 1) to End of study visit

Descriptive analysis (mean, Standard Deviation, Median, Interquartile Range, Minimum and Maximum) of Liver enzymes (SGPT) will be from baseline (visit 1) to End of study visit. Percent change will be calculated between baseline to End of study. Paired t-test will be used to determine *p*-value and significance between baseline and at the end of the study. Unpaired t-test will be used to determine the *p*-value and significance between Changes in Liver enzymes (SGPT) between 2 groups.

10.7.9 Secondary Efficacy analysis:

A. Complete resolution, improvement, failure or relapse of Pelvi- abdominal infection

- Frequency distribution (number & percent) of complete resolution, improvement, failure or relapse for Pelvi- abdominal infection. Chi² test will be used to determine *p*-value and significance between the 2 groups.
- Frequency distribution (number & percent) of improvement for Pelvi- abdominal infection. Chi² test will be used to determine *p*-value and significance between the 2 groups.

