8.5 Other criteria

- To describe presence of any signs/symptoms of post-operative wound infection such as redness, fever or wound discharge.
- To describe presence of undesirable effects on total leukocyte count and liver enzymes (SGOT & SGPT) between baseline (visit 1) to End of study visit (Follow up 2 V)
- To compare the complete resolution, improvement, failure or relapse of Pelvi-abdominal infection between ciprofloxacin[®] versus combined treatment, based on pelvi-abdominal ultrasound and others
- To compare the number of days for complete healing of post-operative wounds between ciprofloxacin[®] versus combined treatment

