- Frequency distribution (number & percent) of presence of any signs/symptoms of post-operative wound infection such as redness, fever or wound discharge. Chi² test will be used to determine *p*-value and significance between the 2 groups.

B. Change in Total leukocytes count between baseline (visit 1) to End of study visit

- Descriptive analysis (mean, Standard Deviation, Median, Interquartile Range, Minimum and Maximum) of total leucocyte will be from baseline (visit 1) to End of study visit. Percent change will be calculated between baseline to End of study. Paired t-test will be used to determine p-value and significance between baseline and at the end of the study. Unpaired t-test will be used to determine the p-value and significance between Changes in total leucocyte between 2 groups.

C. Change in Liver enzymes (SGOT) between baseline (visit 1) to End of study visit

- Descriptive analysis (mean, Standard Deviation, Median, Interquartile Range, Minimum and Maximum) of Liver enzymes (SGOT) will be from baseline (visit 1) to End of study visit. Percent change will be calculated between baseline to End of study. Paired t-test will be used to determine p-value and significance between baseline and at the end of the study. Unpaired t-test will be used to determine the p-value and significance between Changes in Liver enzymes (SGOT) between 2 groups.

D. Change in Liver enzymes (SGPT) between baseline (visit 1) to End of study visit

- Descriptive analysis (mean, Standard Deviation, Median, Interquartile Range, Minimum and Maximum) of Liver enzymes (SGPT) will be from baseline (visit 1) to End of study visit. Percent change will be calculated between baselines to End of study. Paired t-test will be used to determine p-value and significance between baseline and at the end of the study. Unpaired t-test will be used to determine the p-value and significance between Changes in Liver enzymes (SGPT) between 2 groups.

8.9 Secondary Efficacy analysis:

A. Complete resolution, improvement, failure or relapse of Pelvi- abdominal infection

- Frequency distribution (number & percent) of complete resolution, improvement, failure or relapse for Pelvi- abdominal infection. Chi² test will be used to determine p-value and significance between the 2 groups.
- Frequency distribution (number & percent) of improvement for Pelvi- abdominal infection. Chi² test will be used to determine p-value and significance between the 2 groups.

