- Frequency distribution (number & percent) of failure for Pelvi- abdominal infection. Chi² test will be used to determine p-value and significance between the 2 groups.

- Frequency distribution (number & percent) of relapse for Pelvi- abdominal infection. Chi² test will be used to determine p-value and significance between the 2 groups.

B. Days for complete healing of post-operative wounds after 8 days of treatment (Follow up 1 visit) & 15 days of treatment (Follow up 2 visit or End of study visit)

- Descriptive analysis (mean, Standard Deviation, Median, Interquartile Range, Minimum and Maximum) of days for complete healing versus combined treatment will be after 8 days of treatment (Follow-up 1 V) & 15 days of treatment (End of study visit). Percent change will be calculated between baseline to End of study. Paired t-test will be used to determine p-value and significance between baseline and at the end of the study. Unpaired t-test will be used to determine the p-value and significance between Changes in complete healing between 2 groups.

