9.5 Secondary End Point

9.5.1 Secondary Safety:

Table 11 *Number and percent of signs/symptoms of post-operative wound infection among treatment groups*

	Group A (N=156)	Group B (N=156)	p-value
No of signs/symptoms of post-operative wound infection, N (%)			
Redness, N (%)			
Fever, N (%)			
Wound discharge, N (%)			

Table 12 *Percent Change in mean Total leukocytes among treatment groups*

	Group A (N=156)	Group B (N=156)	p-value
Visit 1, mean ± SD			
End of study visit, mean ± SD			
% Change			
p-value between V1 & End of study visit			
p-value between 2 groups			

Table 13 *Percent Change in mean SGOT among treatment groups*

	Group A (N=156)	Group B (N=156)	p-value
Visit 1, mean ± SD			
End of study visit, mean ± SD			
% Change			
p-value between V1 & End of study visit			
p-value between 2 groups			

Table 14 *Percent Change in mean SGPT among treatment groups*

	Group A (N=156)	Group B (N=156)	p-value
Visit 1, mean ± SD			
End of study visit, mean ± SD			
% Change			
p-value between V1 & End of study visit			
p-value between 2 groups			

9.5.2 Secondary Efficacy:

Table 15 Number and percent of complete resolution, improvement, failure or relapse for Pelvi- abdominal infection among treatment groups

	Group A (N=156)	Group B (N=156)	p-value
Complete resolution, N (%)			
Improvement, N (%)			
Failure or relapse, N (%)			

Table 16 *Percent Change in mean days for complete healing of post-operative wounds after 8 days of treatment (Follow up 1 visit) among treatment groups*

	Group A (N=156)	Group B (N=156)	p-value
Visit 1, mean ± SD			
Follow up 1 visit, mean ± SD			
% Change			
p-value between V1 & Follow up 1 visit			
p-value between 2 groups			

Table 17 *Percent Change in mean days for complete healing of post-operative wounds after 15 days of treatment (Follow up 2 visit or End of study visit) among treatment groups*

	Group A (N=156)	Group B (N=156)	p-value
Visit 1, mean ± SD			
Follow up 2 visit, mean ± SD			
% Change			
p-value between V1 & Follow up 2 visit			
p-value between 2 groups			

10 Reference:

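### Nine or ten secondary between-arm tests are each called significant at p<0.05 with no order, adjustment or exploratory label, giving about a 37–40% chance of a false result if they are independent and about 17% at an assumed correlation of 0.8

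*SAP*

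**What the plan says.** SAP 8.3.2 sets one rule for everything: "All tests will be performed on the 5% level of significance", and "P-values less than 0.05 will be considered statistically significant". Protocol 10.7.3 has the same two statements. Neither limits them to the primary endpoints.

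SAP 8.8 and 8.9 then give each secondary variable a test between the arms. Examples:

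- Leukocytes (SAP 8.8): "Unpaired t-test will be used to determine the p-value and significance between Changes in total leucocyte between 2 groups". SGOT and SGPT are treated the same way.
- Relapse (SAP 8.9): "Frequency distribution (number & percent) of relapse for Pelvi- abdominal infection. Chi² test will be used to determine p-value and significance between the 2 groups". The overall outcome distribution, improvement and failure each get the same kind of test.
- Wound-infection signs: in protocol 10.7.8 the frequency table is followed by "Chi² test will be used to determine *p*-value and significance between the 2 groups". SAP 8.8 does the same.

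SAP 8.5 gives a narrower aim for two of these items. For wound signs it is "To describe presence of any signs/symptoms of post-operative wound infection such as redness, fever or wound discharge", and laboratory effects are likewise to be described. Protocol 10.7.5 agrees. The other two items in that list, infection outcome and days to healing, are to be compared.

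Neither document gives a testing order for secondary endpoints, makes them depend on a primary result, adjusts for their number or calls them exploratory.

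**The concern.** Leaving secondary endpoints unadjusted is common and acceptable when they are presented as exploratory. This plan instead says in advance that any of them with p<0.05 is statistically significant.

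Both arms receive the same two active ingredients, so a small or absent difference is plausible on many variables. Under the plan, one chance result could be reported as a significant advantage of the combined tablet, whatever the primary analyses show. A chance laboratory difference could equally be reported as a significant signal against it. The final report is to follow protocol section 10.7, so the rule carries straight into the reported claims.

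**Working it through.** The plan states no family-wise error rate, so there is no figure of its own to reproduce here. The sample size of 312 does not enter this calculation.

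**Step 1: count the tests between arms.** Within-arm paired tests and primary tests are left out.

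| Secondary variable | Analysis text | Tests in text | SAP table shells |
|---|---|---|---|
| Wound-infection signs | SAP 8.8 A | 1 | Table 11: 4 rows |
| Leukocytes, SGOT, SGPT | SAP 8.8 B–D | 3 | Tables 12–14: 3 |
| Infection outcome: overall, improvement, failure, relapse | SAP 8.9 A | 4 | Table 15: 3 rows |
| Days to complete healing | SAP 8.9 B | 1, or 2 by visit | Tables 16–17: 2 |
| **Total** | | **9 or 10** | **12 if every row is tested** |

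The complete-resolution row of Table 15 repeats the primary result in Table 9. Without it the shells give 11.

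**Step 2: independent tests, no true difference, each at two-sided 5%.** The plan does not state sidedness; two-sided is assumed. The chance of at least one p<0.05 is 1 − 0.95^k:

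- k = 9: 1 − 0.630 = 37.0%
- k = 10: 1 − 0.599 = 40.1%
- k = 11: 43.1%
- k = 12: 46.0%

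**Step 3: correlated tests.** The documents give no correlations, so a range is assumed. Sets of k two-sided z-tests with a common correlation were simulated 400,000 times:

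| k | Independent (Step 2) | Correlation 0.5 | Correlation 0.8 |
|---|---|---|---|
| 9 | 37.0% | 27.0% | 16.5% |
| 10 | 40.1% | 28.8% | 17.4% |
| 12 | 46.0% | 31.9% | 18.6% |

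A common correlation of 0.8 across infection outcome, wound signs, leukocytes and liver enzymes is severe, because these measure different things. As a cross-check, suppose infection outcome, wound outcome, liver enzymes and leukocytes each behaved as a single test. The result is 1 − 0.95^4 = 18.5%.

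**Step 4: a false result favouring the combined tablet.** If each test splits its error equally, 2.5% falls on that side:

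- k = 9: 1 − 0.975^9 = 20.4%
- k = 10: 1 − 0.975^10 = 22.4%

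This is approximate, because the overall chi-square on outcome categories has no single direction.

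**Step 5: sparse categories.** When events are rare, the uncorrected chi-square test rejects less often than 5%. At an assumed 1% event rate its true size is 0.7% with 78 per arm and 3.1% with 156 per arm. At 2% it is 3.0% and 4.5%. If failure and relapse each had size 0.7% and the other seven tests kept 5%, nine independent tests would give 1 − 0.95^7 × 0.993^2 = 1 − 0.698 × 0.986 = 31%.

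**The case against.** The best case for leaving the plan alone has five parts.

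- **Labelling.** Endpoints are called primary and secondary throughout, and SAP 8.4 separates main from other criteria. This stands: a reader can tell which results are secondary. A tier of endpoints is still not a testing rule, and the p<0.05 sentence covers both tiers.
- **What the 5% means.** The plan's 5% is per test, and neither document promises family-wise control of secondary endpoints. A reader might infer from the figures above that the plan exceeds its own error rate several times over. The documents do not support that, because a family-wise rate and a per-test level are different quantities.
- **The count.** A reader might infer from the shells that 12 tests, and so 46%, are planned. Tables 11 and 15 have one blank p-value column each; Table 15 could carry a single chi-square, and one of its rows is a primary variable. The firm count is the 9 or 10 in the analysis text.
- **Safety.** Four of the nine tests are safety comparisons, where strict adjustment could hide harm. This is a good reason not to adjust them. It is not a reason to declare them significant. Secondary efficacy alone, with 5 or 6 tests, still gives 1 − 0.95^5 = 23% to 1 − 0.95^6 = 26% if independent.
- **Later SAP.** SAP 8.2 foresees a final SAP before database lock. The SAP at hand repeats the rule unchanged, so that provision is the route for the correction rather than an answer to it.

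**Conclusion.** The point holds as a defect in the stated decision rule for secondary endpoints. Nine or ten between-arm tests are to be called significant at an unadjusted p<0.05, including tests on variables that the same documents say are only to be described.

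With no true difference, the chance of at least one such result in either direction is about 37–40% if the tests are independent, about 27–29% at a correlation of 0.5 and about 17% at 0.8. The correlations are assumptions, and the last value is close to a floor. For a result favouring the combined tablet, the chance is about 20–22% if independent. Sparse outcome categories would lower these figures somewhat.

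A reader might go further and infer that the trial's main conclusion is compromised. Nothing here supports that, because only the secondary family is concerned. The change should be made, but the primary analyses do not depend on it.

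**What to change.** Add to SAP 8.3.2, 8.8 and 8.9 and to protocol 10.7.3, 10.7.8 and 10.7.9: *Secondary comparisons are exploratory; they are reported as between-arm estimates with 95% confidence intervals, p-values are nominal, and no claim of statistical significance is made.* In SAP 8.3.2 and protocol 10.7.3, limit the p<0.05 significance sentence to the primary endpoint analyses. This also brings the analysis sections into line with the descriptive aims in SAP 8.5 and protocol 10.7.5, and no safety information is lost.

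Keeping one secondary claim, tested only after the primary succeeds, would not work as the plan stands. There are several primary tests and no rule for what counts as success. Days to healing, an obvious candidate, is analysed as a change from Visit 1, but the protocol's schedule of visits collects it only at Day 8 and Day 15.

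The cost is wording in two documents. The one small downside is that the sponsor gives up unadjusted significance claims on secondary variables.
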